### WP 3:

We will use the Framework approach (with an initial framework based on the main domains covered by the interview schedule (i.e. positive vs negative experiences, facilitators vs barriers, and areas for future innovation and development) to analyse interview data in the following stages:

- familiarisation by listening to the recording and reading transcripts of the interviews in order to list key ideas and recurrent themes;

- identifying a thematic framework by drawing on issues identified from our previous studies as well as views or experiences expressed in the data, providing an initial index of codes and themes;
- indexing by annotating the transcripts with codes, subthemes and themes supported by NVivo;
- charting, by rearranging data according to the appropriate part of the thematic framework to which they relate, to form charts;
- mapping and interpretation by using the charts to define concepts, map the range and nature of themes, as well as interactions and relations between them, to provide rich descriptions and explanations for the findings.
- Where possible we will also compare perspectives of patients, relatives, CFRs and ambulance staff of the same event where a CFR attended, to look for shared or contrasting views.

#### WP 4:

We will synthesise the quantitative and qualitative data from each site which will enable us to describe an 'actor-based system map' for each setting consisting of current people, structures, processes and relationships between rural CFRs, patients and other health and social care staff and providers in each setting, comparing and contrasting features between the sites.

We will use a number of techniques at the integration stage. At the analysis stage we will use the technique of 'following a thread', employing an iterative approach to compare and explore findings from the QUAN (WP1 and 2) and QUAL (WP3) work packages. Next, we will use a matrix to compare and contrast QUAN and QUAL (documentary information on guidelines, policies and protocols together with interview) data at each ambulance site to gain a whole-case perspective. Finally, we will use triangulation protocol to allow us to list overall findings from QUAL and QUAN work packages to explore whether there is agreement (convergence), related information on a particular issue (complementarity), discrepancy in findings (dissonance) or silence (findings relate only to QUAL or QUAN analysis).

We will articulate a change agenda for the CFR role, based on interview data, describing the health and social care problems identified at each site expressed through the needs and views of patients, staff and other stakeholders. We will also synthesise data describing potential developments and innovations in the CFR role to solve these problems, the conditions which would need to be modified to bring change about, and transformations in structures, processes and relationships which would sustain such changes in the longer term.

Through the integration of data we will also develop possible causal impact pathways, theories of action (pathways and interventions promoting actor-level change) and the theory of change (i.e., the ways in which actor-level changes could lead to systems changes and impacts).

#### WP 5:

Data analysis is not required in WP 5.

## **STUDY SETTING**

We will conduct the study in seven rural NHS ambulance trusts which will enable us to cover most of rural England:

- East Midlands Ambulance Service (EMAS)
- West Midlands Ambulance Service (WMAS)
- Yorkshire Ambulance Service (YAS)
- South Central Ambulance Service (SCAS)
- North West Ambulance Service (NWAS)
- South East Coast Ambulance Service (SECAMB)
- South West Ambulance Service Foundation (SWAST)

These NHS Trusts have confirmed their participation and have committed to support the study. London Ambulance Service NHS Trust was not included as it is mainly urban; East of England Ambulance Service and North East Ambulance Service were not included due to a lack of electronic data.

## **SELECTION OF PARTICIPANTS**

### **ELIGIBILITY CRITERIA**

Work package 3 will involve the active recruitment of participants for interviews.

Participants will include adult patients, relatives, CFRs and ambulance staff identified from records of patients who have been attended by a CFR in a rural location in the previous six months. Where possible we will interview patients, relatives, CFRs and ambulance staff attending the same event. GPs will be purposively sampled from rural areas of the ambulance services involved plus we will endeavour to interview ambulance service commissioners and CFR leads.

If patient and relative recruitment proves to be difficult, then we will also recruit via social media advertisement.

If ambulance staff and CFR recruitment proves to be difficult then we will also have the option to recruit via internal adverts/emails/social media for each ambulance service involved in the study and their associated CFR schemes.

### **Inclusion Criteria**

Adults capable of giving informed consent (above the age of 18 years with no upper age limit).

We will recruit a maximum variation sample of patients (according to age, sex, condition, and ethnicity), ambulance staff (sex, experience, ethnicity and role), CFR (sex, ethnicity, length of experience, skill level) and CFR scheme leads (independent charity and ambulance trust overseen schemes).

### **Exclusion Criteria**

We will exclude children and adults who are unable to give informed consent from this study.

London Ambulance Service NHS Trust is not included as it is mainly urban; East of England Ambulance Service and North East Ambulance Service are not included because of lack of electronic data.

## **Sampling**

Samples are only required for work packages 1 and 3.

### **WP1:**

For East Midlands Ambulance Service NHS Trust (EMAS) we have available data to estimate the numbers of records. For all emergency attendances during one year between April 2018-Mar 2019, CFRs attended 17,919 of 636,211 (3%) calls.

The five other ambulance trusts supplying data to the study have similar numbers of total attendances (i.e. 600,000-750,000) based on national data.

Therefore, we estimate around 100,000 CFR-patient contacts across 6 ambulance trusts in one year. A proportion of these are likely to be rural. Based on analysis of a sample of data from a dataset we have previously analysed our estimate of rurality is that it is a factor in approximately 50% of calls.

Our total available sample for analysis is estimated to be at least 50,000 incidents across 6 ambulance trusts meaning that self-identification of individual patients will not be possible.

### **WP 3:**

We will purposively sample patients, relatives, and ambulance staff identified from records of patients who have been attended by a CFR in a rural location in the previous six months. Where possible we will interview patients, relatives, CFRs and ambulance staff attending the same event. GPs will be purposively sampled from rural areas of the ambulance services involved. We will recruit a maximum variation sample of patients (according to age, sex, condition, and ethnicity), ambulance staff (sex, experience, ethnicity and role), CFR (sex, ethnicity, length of experience, skill level) and CFR scheme leads (independent charity and ambulance trust overseen schemes).

Should patient and relative recruitment prove difficult, then we will also advertise the study via social media.

If ambulance staff and CFR recruitment proves to be difficult, then we will also have the option to recruit ambulance staff, CFRs and CFR leads via internal adverts/emails/social media for each ambulance service involved in the study and their associated CFR schemes.

## **Size of sample**

### **WP 1 Sample size:**

The sample size for a univariate regression model with uncorrected  $\alpha=5\%$  and 6 predictor variables predictors (call type, clinical condition, age, sex, ethnicity, rurality) with one main outcome (transportation to hospital) and a change in  $R^2=0.001$  at 90% power is estimated to be 9472. To account for multiple-test correction we used Bonferroni correction to set  $\alpha$  at

0.83% for the significance level. This will give a sample size of 13,824 at 90% power and a sample size of 11,008 at 80% power.

Data from around 50,000 incidents will provide a representative and generalisable sample for the multivariable analysis.

One ambulance trust (North West Ambulance Service NHS Trust) are unable to provide electronic data for the study but will be able to participate in other aspects of the research and has therefore been included.

### WP 3 Sample size:

We will plan for around 60 interviews comprising approximately 15-20 interviews of patients (and/or relatives), 15-20 interviews of CFRs/CFR leads and 15-20 interviews ambulance staff, with additional interviews of GPs and/or commissioners (10-15) including each of the participating ambulance services. Recruitment will continue until we have completed a total of approximately 60 interviews, continuing to data saturation.

### WP 3:

WP 3 is the only package in this study where participants will be actively recruited.

### WP 3 Primary recruitment method:

Our primary method of recruitment will be to: purposively sample patients, relatives, and ambulance staff identified from records of patients who have been attended by a CFR in a rural location in the previous six months. Where possible we will interview patients, relatives, CFRs and ambulance staff attending the same event. GPs will be purposively sampled from rural areas of the ambulance services involved. We will recruit a maximum variation sample of patients (according to age, sex, condition, and ethnicity), ambulance staff (sex, experience, ethnicity and role), CFR (sex, ethnicity, length of experience, skill level) and CFR scheme leads (independent charity and ambulance trust overseen schemes).

Ambulance services will assist us with identifying and contacting participants using our primary method of recruitment. Ambulance services will also check in advance with GPs that it is appropriate to contact any participants who are former ambulance service patients. This is to avoid contacting patients who the GP considers are too ill to participate or to avoid inadvertently contacting and potentially causing distress to, relatives of patients who have died.

Any initial approach to patients using the primary method (prior to their consent) will not be made outside the clinical care team. At initial approach all participants will be provided by the ambulance service with an information sheet and consent form about/for the study (either by post or email/online) and invited to contact the research team at university of Lincoln if they have further questions.

On receipt of returned consent forms, a member of the research team will contact potential participants by telephone/letter/email to verify study eligibility, answer any further questions the participants may have and reconfirm informed consent. At this stage the researchers will also schedule a face-to-face or telephone interview at a place and time convenient to the participant.

Under the General Data Protection Regulation (GDPR), East Midlands Ambulance Service NHS Trust (EMAS) is the Data Controller for any personal information it processes. EMAS seeks general consent for sharing anonymised or pseudo-anonymised patient information for research purposes. Patients can withdraw consent for use of data at any time if they change their mind. EMAS always removes any information that may identify individual patients from anonymised or pseudo-anonymised datasets. Accordingly, statistical information, requiring anonymised data, will be used in this study. All other ambulance services will follow similar GDPR practices.

### WP 3 Secondary recruitment methods:

We will also have the option to use social media to advertise the study to patients and their relatives as a secondary recruitment method, should recruitment of patients and relatives prove difficult using our primary method outlined above. This will give patients and relatives who are eligible, the opportunity to initiate contact directly with the research team, should they be interested. The social media advert for the study will take interested participants to either an online form or a telephone contact where they can go through an eligibility checklist. The eligibility checklist will check:

- County – to check whether they are in one of the permitted ambulance service areas. If not, they are not eligible.
- That they or their relative have made a call to an ambulance service within the previous 6 months for an emergency where a CFR attended.
- Age ( $\geq 18$  years)

If they meet the eligibility criteria, then they will be asked to provide contact details for a phone call when formal consent will be taken for a telephone interview. A participant information sheet will also be sent to them prior to interview.

We will also have the option to use participating ambulance service and CFR scheme internal adverts/emails/social media to invite CFRs, CFR scheme leads and ambulance staff to take part in interviews.

All study documentation will be provided in English. If needed, ambulance service and translator services will be available where possible to assist with discussion of the trial, the participant information sheets, and consent forms, but the consent forms and information sheets will not be available printed in other languages.

It will be explained to the potential participants that entry into the study is entirely voluntary and that their treatment and care will not be affected by their decision. It will also be explained that they can withdraw at any time but attempts will be made to avoid this occurrence. In the event of their withdrawal it will be explained that their data collected so far may not be erased in accordance with the University's Research Privacy Notice and information given in the Participant Information Sheet and we will seek consent to use the data in the final analyses where appropriate.

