## STUDY SUMMARY

Study Title	Community First Responders' role in the current and future rural health and care workforce (The CFR Study).
Study Design	Mixed methods with 5 linked work packages (WPs).
Study Participants	Patients/relatives, ambulance staff, GPs, commissioners, Community First Responders (CFRs) and CFR leads (these participants are involved in Work packages 1 and 3).
Eligibility Criteria	
Patients (and their relatives) who have been attended by a CFR.
 
Staff as defined above in study participant list.

Planned Sample Size	
Work package (WP) 1: Anonymised data from around 50,000 incidents will provide a representative and generalisable sample for the multivariable analysis. Sample size= 13,824 at 90% power and 11,008 at 80% power.
 
Work package (WP) 3: 60 interviews comprising approximately: 15-20 interviews of patients (and/or relatives), 15-20 interviews of CFRs/CFR leads and 15-20 interviews ambulance staff, with additional interviews of GPs and/or commissioners (10-15).

Study Duration	
Participant duration: In work package 3 participants will be approached for a one-off interview lasting 60 minutes for patients and 40 minutes for staff.
 
Total study duration: 30 months.

Objectives	
Work package 1: Describe contribution of CFRs to rural health provision in terms of numbers/timing of calls attended, types of condition and people attended.
 
Work package 2: Evaluate costs, funding sources, and consequences of CFR schemes.
 
Work package 3: Analyse CFR guidelines. Explore stakeholder (patients, relatives, ambulance staff, primary care, commissioners, CFRs and CFR scheme organisers) experiences and perceptions of CFRs' current role and potential for future developments/innovations.
 
Work package 4: Assimilate and integrate data from WPs 1-3.
 
Work package 5: Prioritise recommendations for future developments/innovations in rural CFR provision through a consensus stakeholder workshop.

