## **STUDY OBJECTIVES AND PURPOSE**

### **PURPOSE**

We aim to work with PPI and stakeholders throughout to develop recommendations for future innovations in rural CFR provision by investigating current activity, costs of provision, and views of patients, public, CFR schemes and rural care providers.

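### The fallback social-media checklist for WP3 patients and relatives omits the rural condition that the other WP3 recruitment text applies, so people attended at non-rural incidents can pass screening

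*Protocol*

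**What the plan says.** The rural condition appears in three places in the protocol. Under Eligibility Criteria, WP3 patients, relatives, CFRs and ambulance staff are "identified from records of patients who have been attended by a CFR in a rural location in the previous six months". WP 3 Primary recruitment method again starts from "patients who have been attended by a CFR in a rural location in the previous six months", and the WP 3 paragraph under Sampling repeats this. The stated Purpose of the study is to "develop recommendations for future innovations in rural CFR provision".

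WP 3 Secondary recruitment methods adds an optional social-media route for patients and relatives, to be used if the primary route proves difficult. It lists what the eligibility checklist will cover:

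- county, "to check whether they are in one of the permitted ambulance service areas";
- a qualifying event: the respondent or a family member must "have made a call to an ambulance service within the previous 6 months for an emergency where a CFR attended";
- age 18 or over.

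The next step is: "If they meet the eligibility criteria, then they will be asked to provide contact details for a phone call when formal consent will be taken". That consent is for a telephone interview. No rural item is listed, and no later check of rurality is stated for this route.

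**The concern.** The checklist keeps the adult, six-month and CFR conditions of the other sections and leaves out only the rural one. The two routes therefore admit different populations of patients and relatives, although the protocol presents the second as another way of reaching eligible people.

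WP3 interviews supply the change agenda in WP4 and feed its site-level system maps, and the WP4 recommendations go to the WP5 workshop. The background section names service users' views as a gap in earlier work, and only 15-20 interviews are planned for that group. An interview given to someone attended at a non-rural incident uses one of those places. Unless it is recognised and handled, it also brings non-rural experience into conclusions about rural provision.

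**Working it through.** The check is mainly a comparison of texts.

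**Conditions by route, patients and relatives**

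| Condition | Eligibility Criteria, Sampling (WP 3), WP 3 Primary recruitment method | WP 3 Secondary recruitment methods (checklist) |
|---|---|---|
| CFR attended | Yes | Yes |
| Within six months | Yes | Yes |
| Adult | Yes (Inclusion Criteria) | Yes |
| Participating ambulance service | Yes (identified from its records) | Yes (county) |
| Rural location | Yes | Not listed |

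**Can county stand in for rurality?** No. Its stated purpose is to confirm the ambulance service area. Under Sampling (WP1), the protocol estimates that rurality is a factor in about 50% of calls, so being in a participating area does not make an incident rural. Under Recruitment (WP 1), the protocol defines rurality by government classes D1 to F2, and for the EMAS data it links rurality through the incident postcode. That is much finer than county.

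**Is there a later check?** The primary route includes a call in which the researchers verify eligibility. The social-media route goes from checklist to consent call to interview, with no rurality check described.

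**Could non-rural cases be recognised later?** Yes. The WP3 interview topics listed under Study Regimen include where the event took place. This comes after the interview slot has been used, and neither the WP3 analysis text nor the WP4 text says what to do with a non-rural account.

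**Size, as an illustration only.** The protocol gives no figure to reproduce. Let n be the planned patient/relative interviews, s the share of them recruited by social media, and r the rural share among those recruits.

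Expected non-rural interviews = n × s × (1 − r)

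- n = 15 to 20 (WP 3 Sample size).
- s is not given. It is 0 if the route is never used; 0.25 is assumed here.
- r is not given for social-media responders. The WP1 figure of 0.50 for calls is borrowed as an assumption.

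With s = 0.25 and r = 0.50:

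- 15 × 0.25 × 0.50 = 1.9
- 20 × 0.25 × 0.50 = 2.5

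Varying r from 0.75 to 0.25 at the same s gives 15 × 0.25 × 0.25 = 0.9 up to 20 × 0.25 × 0.75 = 3.75. That is roughly 1 to 4 interviews. At s = 0 the answer is 0.

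**The case against.** The strongest reply is that the contradiction is softer than the comparison suggests. The Study Summary requires only patients and relatives "who have been attended by a CFR", and the Inclusion Criteria add no rural condition. Under Eligibility Criteria the rural phrase is attached to identification from records, with social media then added as a separate route. A deliberately wider fallback is therefore a possible reading. WP3 is also a purposive, maximum-variation qualitative sample that estimates no proportions, and the route may never be used.

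Part of this stands. The route is conditional, so non-rural respondents can pass screening; the protocol does not show that they will. But nowhere does it say that the fallback is meant to widen the population. It describes the route as one for patients and relatives who are eligible, and it calls the checklist items eligibility criteria ("If they meet the eligibility criteria, then they will be asked to provide contact details for a phone call"). The missing qualifier in the Study Summary and Inclusion Criteria shows that the rural condition is applied unevenly. It does not authorise a second population.

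A reader might infer four stronger things that the protocol does not support:

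- **That non-rural interviews could never be identified.** The interview schedule asks where the event happened.
- **That anyone attended in a town is wrongly admitted.** The Town and Fringe classes D1 and D2 count as rural in this protocol.
- **That half of all patient/relative interviews, 8-10, would be non-rural.** This needs the fallback to supply the whole quota and responders to mirror a share estimated for WP1 calls. The protocol supports neither.
- **That adverts to CFRs and ambulance staff have the same fault.** Eligibility Criteria allow those adverts without stating a rural-incident test for each person, and these groups attend many incidents.

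**Conclusion.** The point holds for patients and relatives recruited through social media. The checklist, followed as written, can admit people whose incident was outside the protocol's rural classes, while the eligibility, sampling and primary recruitment sections select on a rural attendance. Such cases could be recognised at interview, but no rule for excluding or labelling them is stated.

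The number affected is unknown. It is zero if the route is not used, and about 2 of 15-20 if a quarter of these interviews come this way and half of those are non-rural. Both of those shares are assumptions. The effect is on how well the WP3 patient/relative sample fits a rural question and on what passes from it into WP4. The WP1 sample size and analysis are untouched. This is a modest inconsistency about the study's defining population, and it should be put right because that is cheap to do.

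**What to change.** Add one item to the social-media checklist asking for the place of the incident, either nearest place or postcode. Map it to rural classes D1 to F2 as defined under Recruitment (WP 1), and treat respondents outside those classes as not eligible. Use the answer only for classification and then delete it, in line with the protocol's handling of incident postcodes in WP1.

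If non-rural respondents are meant to be accepted, say so in WP 3 Secondary recruitment methods and in Eligibility Criteria, label their interviews, and keep them out of the rural themes.

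The cost is one more screening question, slightly fewer eligible responders, and an amendment to the screening form. The protocol's own rule on amendments applies: changes to documents that needed ethics approval wait for that approval and for HRA categorisation.
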